10.2 Study Amendments and Study Termination

Amendments to the study must be made only by prior agreement between the Amicus Therapeutics and Open Health. The Independent Ethics Committee (IEC)/Institutional Review Board (IRB) must be informed of all amendments and give approval for substantial amendments. The local Principal Investigator is responsible for obtaining approval from the IEC/IRB, and the local Clinical Research Organisation (CRO) supporting them will ensure a copy is forwarded to Amicus Therapeutics.

Open Health, Amicus Therapeutics and Principal Investigators reserve the right to terminate participation in the study according to the study contract. Open Health will notify the IEC/IRB in writing of the study's completion or early termination and send a copy of the notification to Amicus Therapeutics.

11. Protection of human subjects

This study will comply with all applicable laws, regulations, and guidance regarding patient protection including patient privacy, and consistent with the ethical principles of the Declaration of Helsinki²⁴, the requirements of the General Data Protection Regulation (GDPR)²⁵ and any other relevant local regulations. This study has been designed to minimise the data collected to that which is required for the planned analyses. The data collected will not include any direct identifiers. Data will be transferred to, and held securely by, Open Health at their offices within the UK during the conduct of this study, supported as needed by their local partners (refer to section 0).

11.1 Ethical and regulatory approvals

IEC/IRB approvals, competent authority and local management approvals for the conduct of this study and the sharing of anonymised-coded patient and caregiver data will be sought according to applicable local regulations.

11.2 Ethical considerations

This is an observational study involving a prospective time and motion study, completion of questionnaires by patients with FD and their caregivers and collection of demographic data from medical records; there will be no changes to patient management and no additional visits are required for the study. Only anonymised-coded data will be collected.

A participant information sheet will be provided to patients and caregivers identified as being eligible for study participation by the patient's whole care team, explaining the above components of this research study. Only patients providing written informed consent (for one or both components) will be included in the study and no data collection will take place until written informed consent for the relevant component of the study has been provided. Caregivers will only be included if the patient with FD for whom they provide care or support has also consented to join the study. HCPs at the participating centres will give consent to be observed in their provision of care for the time and motion study.

Patient- and carer-reported outcome data will be collected prospectively for those providing informed consent. Participation requires patients to complete a ~25-30 minute series of questionnaires related to the impact of FD on HRQoL, wellbeing, levels of fatigue and work productivity, which some may find upsetting. As most patients will complete the validated questionnaires during an ERT infusion, their HCPs will be able to provide support in the event that they do experience any distress. There will be no direct benefits of participation in the study but patients will be provided with a name and contact details for study-related queries.

Patients and caregivers will be able to withdraw from the study at any time without any impact on the patient's clinical care.

11.3 Participant privacy

The Data Controller for this study is Amicus Therapeutics. Data will be collected in anonymised-coded format and no personally identifiable information on any participant will be collected or removed from the hospitals or treatment centres participating in the study in order to preserve patient confidentiality. Participants will be assigned a study-specific unique identification number which will be referenced in a study log. This identification log will not leave the participating centre location and will be the responsibility of the principal investigator at that study centre. Anonymised-coded participant data will be processed for the purposes of the research study described in this protocol and will be shared with Amicus Therapeutics, Open Health, Klinikos, Zeincro and IQVIA within the European Economic Area (EEA) and, intellim Holdings Corporation and Clinical Trial & Consulting based outside the EEA for the purposes of this research study. Companies located outside the EEA will maintain anonymised-coded data in accordance with the recognised EU Model Clause Agreement to

safeguard participant anonymity. Participant data will be retained for the archive period specified in section 11.4. Participants will be advised of their rights in respect of their data, including the right to raise any concerns or complaints related to this research study with the applicable local data protection regulator.

11.4 Study Documentation and Archive

Consistent with ENCePP/ISPE/GDPR guidance, the study documents and anonymised-coded data will be archived securely by Open Health on behalf of Amicus Therapeutics for a period of three years in the UK after the end of the study (defined as the date of the final signed Study Report). After this time, the electronic patient-level study data will be removed of unique study codes (i.e. completely anonymised) and transferred securely to Amicus Therapeutics for extended archiving in line with their standard archive period for non-clinical trials. All other study documents will, with Amicus Therapeutics approval, be securely destroyed. The duration of archiving of study data will ensure that any queries arising from peer review of any ensuing publications can be addressed by reference to the source data if required.

12. Management and reporting of adverse events / adverse reactions

No patients will have received treatment with any Amicus Therapeutics medicinal products as part of this study, therefore it is not anticipated that Adverse Events (AEs), as defined below, will be required to be reported for study patients.

However, any AEs reported by an HCP in relation to patients that have received an Amicus Therapeutics product in the course of normal clinical practice will be reported in line with the guidance below. These events will be summarised in the safety reporting section of the final study report.

Sites will be advised that any untoward medical occurrence in a patient in this study following administration of a non-Amicus Therapeutics medicinal product should be reported as an AE to the authority marketing the product by the patient's HCP as per their local regulatory requirements.

12.1 Definitions

Adverse Event: Any untoward medical occurrence in a patient or clinical trial subject administered a medicinal product and which does not necessarily have a causal relationship with this treatment.

Adverse Drug Reaction (ADR):

As per the definition found in the WHO Technical Report 498 [1972], an adverse drug reaction is a response to a drug which is noxious and unintended and which occurs at doses normally used in man for prophylaxis, diagnosis, or therapy of disease or for modification of physiological function

Product Complaints (PCs):

Product Quality Complaint (PQC) – Any communication that alleges deficiencies related to the drug product as a result of manufacturing, packaging, or distribution and calls into question the identity, strength, quality, potency, purity, tampering and/or counterfeiting of that marketed drug product . Product Quality Complaints (PQCs) can involve reports of product defects, such as product appearance, packaging issues, taste/odour etc. PQCs can also contain adverse events e.g., lack of efficacy (failing to produce the expected pharmacological action for the approved indication).

Non-Product Quality Complaint:

A complaint that does not directly relate to product quality, purity, strength, potency, safety or effectiveness, such as a service complaint.

Product Safety Events:

Post marketing Safety Events collectively refer to:

- All reports of AEs (non-serious and serious)
- AEs associated with product complaints, or counterfeit products
- Exposure during pregnancy and lactation (including paternal)
- Reports of overdose, misuse, abuse, drug interaction
- Medication error
- Off-label use with or without an AE
- Lack of efficacy
- Occupational exposure
- Suspected transmission of an infectious agent

Clinical trial safety events refer to:

Events specified to be collected and reported to Amicus pharmacovigilance (or designee) within the study protocol. This may include, but is not limited to serious adverse events, pregnancies, and overdose reports.

Serious Adverse Event:

A serious adverse event (experience) or reaction is any untoward occurrence that at any dose results in any of the following:

- Life-threatening AE: (an event in which the patient was at risk of death at the time of the event; it does not refer to an event which hypothetically might have caused death if it were more severe)
- Death
- Inpatient hospitalization or prolongation of existing hospitalization
- Persistent or significant disability/incapacity
- Congenital anomaly/birth defect
- Medically significant: (events that may not be life-threatening, result in death, or require hospitalization but may be considered serious when, based upon appropriate medical judgment, they may jeopardize the patient or subject or may require medical or surgical intervention to prevent one of the outcomes listed in this definition above).

Special Situations (SS):

Circumstances where the report does not include an AE *per se*, but nevertheless needs to be reported to Amicus Therapeutics. These circumstances include as per GVP module VI (use in a paediatric or elderly population, overdose, off-label use, abuse, misuse, medication error, lack of therapeutic effect /lack of effect (LOE), occupational exposure, falsified medicinal product, suspected transmission of an infectious agent via a product, drug interactions (including drug/food, drug/device, and drug/alcohol interactions, drug/food interactions), unexpected therapeutic effect, or worsening of an existing condition

Unexpected Therapeutic Effect: a beneficial therapeutic effect of a Product aside from the use for which it had been given

12.2 Reporting Procedures for Adverse Events

12.2.1 Reporting Time-Frames

OPEN VIE shall report all potential AEs, SSs, and all PCs to Amicus within 24 hours of receipt of the event and no later than 1 business day. Reporting responsibilities are the same for all

AEs, irrespective of the seriousness of the event or whether or not it was caused by the product. All SSs, and PCs should be reported, whether or not there is an associated AE.

12.2.2 Reporting methodology

AEs, SSs, and PCs should be reported via email to [contact] .

12.3 Reconciliation

At the end of the study (defined as after all study data is entered into the eCRF), IQVIA will email a report of cases received at IQVIA during the study to OPEN VIE. OPEN VIE is required to review the listing of cases and respond to IQVIA within 1 business day, confirming either that the list is correct or highlighting any discrepancies between the listing received from IQVIA and OPEN VIE records. Should OPEN VIE note that case reports are missing from the list provided by IQVIA, OPEN VIE will forward the missing report(s) within 1 business day via email to IQVIA at [contact]. IQVIA will follow up any discrepancies to resolution.

13. Plans for disseminating and communicating study results

Study results will be submitted for presentation at appropriate national and/or international conferences and may also be submitted for publication to appropriate peer reviewed journals; the primary endpoint will be reported in the first publication arising from this study.

The study will be reported according to the requirements of STROBE (Strengthening the reporting of observational studies in epidemiology) as specified in the appropriate checklist for the study design²⁷.

Authorship of any publications arising from the study will follow the guidelines proposed by the International Committee of Medical Journal Editors (2015)³⁰. All authors will meet the criteria for authorship, and all people who meet the criteria will be authors and all authors will agree to be accountable for the study. Potential conflicts of interest will be disclosed. All authors will have:

(1) made substantial contributions to conception or design or acquisition of data, or analysis and interpretation of data; AND

- (2) participated in drafting the publication or revising it critically for important intellectual content; AND
- (3) approved the final version to be published.

Each author will have participated sufficiently in the work to take public responsibility for appropriate portions of the content. Acquisition of funding, collection of data, or general supervision of the research group will not justify authorship.

14. Study support

The study is sponsored by Amicus Therapeutics. Amicus Therapeutics has commissioned Open Health to develop materials for and coordinate the conduct of the study, including protocol development, ethical and local approval, data collection, analysis and presentation of the results.

Reporters Contact Details: First Name Family Name Occupation Address City ZIP/Post-Code Country State Email Tel Fax Signature Date (DDMMYYYY) Treating Doctor (if different from reporter) First Name Family Name Specialty Address City ZIP/Post-Code Country State Email Tel Fax																																										
2. Patient Information 
 
 Initials:	Gender:  Male  Female  Unknown	Date of Birth (DDMMYYYY): Or Age: (Years)	
 
 Height:  cm  m	Weight:  kg  lbs	Ethnic Origin:	
 
 Pregnant:  Yes  No  Not Applicable  Unknown	
 
			Initials:	Gender:  Male  Female  Unknown	Date of Birth (DDMMYYYY): Or Age: (Years)	Height:  cm  m	Weight:  kg  lbs	Ethnic Origin:	Pregnant:  Yes  No  Not Applicable  Unknown																																	
Initials:	Gender:  Male  Female  Unknown	Date of Birth (DDMMYYYY): Or Age: (Years)																																								
Height:  cm  m	Weight:  kg  lbs	Ethnic Origin:																																								
Pregnant:  Yes  No  Not Applicable  Unknown																																										
3. Suspect Product Details 
  
 Drug Name	Indication	Batch No/ Expiry date.	Start Date (DDMMYYYY)	Stop Date (DDMMYYYY or state if ongoing)	Unit Dose	Frequency	Route	
   
 	 	 	 	 	 	 	 	
 
 	 	 	 	 	 	 	 	
 
 	 	 	 	 	 	 	 	
 
 	 	 	 	 	 	 	 	
  
 
Overdose:  Yes  No Administration Error:  Yes  No If Yes please describe in Event Section below.
			Drug Name	Indication	Batch No/ Expiry date.	Start Date (DDMMYYYY)	Stop Date (DDMMYYYY or state if ongoing)	Unit Dose	Frequency	Route																																
Drug Name	Indication	Batch No/ Expiry date.	Start Date (DDMMYYYY)	Stop Date (DDMMYYYY or state if ongoing)	Unit Dose	Frequency	Route																																			

EU/ROW Amicus Adverse Event/Special Situation and Product Complaints Intake Form

Email the completed form to: [contact]

4. Event Details									
Reported Event (list in order of importance)	Onset Date (DDMMYYYY) Time to Onset	Resolved	Stop Date (DDMMYYYY)	Relationship to Suspect Product	Serious				
	 Yes  No  with sequelae			 Unrelated  Possibly  Related	 Unlikely  Probably	 Yes  No			
	 Yes  No  with sequelae			 Unrelated  Possibly  Related	 Unlikely  Probably	 Yes  No			
	 Yes  No  with sequelae			 Unrelated  Possibly  Related	 Unlikely  Probably	 Yes  No			
	 Yes  No  with sequelae			 Unrelated  Possibly  Related	 Unlikely  Probably	 Yes  No			

 Hospitalized/ Hospitalization Prolonged  Death
 
Admission Date (DDMMYYYY):/...../.....
 
Discharge Date (DDMMYYYY):/...../.....
 
Cause:
 
Autopsy performed?  Yes  No
 
Autopsy report enclosed?  Yes  No
									

If reporter is HCP, tick all additional categories that apply:
 
 
  Persistent or Significant Disability/ Incapacity	 Life Threatening	
 
  Congenital Anomaly/ Birth Defect	 Medical / Surgical Intervention to prevent any of the above	
 
						 Persistent or Significant Disability/ Incapacity	 Life Threatening	 Congenital Anomaly/ Birth Defect	 Medical / Surgical Intervention to prevent any of the above
 Persistent or Significant Disability/ Incapacity	 Life Threatening								
 Congenital Anomaly/ Birth Defect	 Medical / Surgical Intervention to prevent any of the above								

Was this event reported with a Product Complaint (PC)?  Yes  No
 
Is the complaint sample available?  Yes  No
 
If Yes, state PC Reference Number (if available):
 
Brief description of PC:
 
.....
									

Additional Information (e.g. overall diagnosis, relevant investigations, previous episodes etc.):
 
Please provide a written summary of the course of the event, including signs, symptoms, severity, treatment and any other assessments which help to explain the event (in case of insufficient space please attach another blank page signed and dated).
 
.....
									

EU/ROW Amicus Adverse Event/Special Situation and Product
Complaints Intake Form

Email the completed form to: [contact]

5. Action Taken	
 Suspect Product Continued	
 Suspect Product Dose Changed as a response to AE? Date of Change (DD/MM/YY):   /...../.....	
 Suspect Product Withdrawn	Date Withdrawn (DD/MM/YY):/...../.....
Symptoms Abated on Suspect Product Withdrawal  Yes  No  N/A	
 Suspect Product Temporarily Withdrawn	Date Withdrawn (DD/MM/YY):/...../.....
Date Restarted (DD/MM/YY):/...../.....	
Symptoms Abated on Product Withdrawal?  Yes  No  N/A	
Symptoms recurred on re-exposure to Suspect Product?  Yes  No  N/A	
 Unknown	
Previous Exposure to Suspect Product?  Yes  No  N/A	
Similar Events After Previous Exposure?  Yes  No  N/A	
Treatment Given:  Yes  No	
If Yes, state: _____	

6. Relevant Medical History (including allergies, surgical procedures etc. that started PRIOR to use of Galafold)			
Condition / Procedure	Start Date (DD/MM/YY)	Stop Date (DD/MM/YY or more if ongoing)	Comment

7. Concomitant Medications			
Concomitant Medication name	Start Date (DD/MM/YY)	Stop Date (DD/MM/YY or more if ongoing)	Comment

17. Annex 2 Study questionnaires

1. ANALYSIS AIM AND OBJECTIVES

1.1 Primary Objective

To quantify the total time spent by HCPs (Health Care Professional) in the preparation and administration of a single dose of ERT (with agalsidase alfa and agalsidase beta) in patients with Fabry disease (FD).

1.2 Secondary Objectives

- To quantify the total patient time (hours/minutes), their costs (i.e. out of pocket expenses) and work-related absence associated with attendances for the administration of a single dose of ERT (with agalsidase alfa and agalsidase beta) in patients with FD.
- To quantify the total caregiver time (hours/minutes), their costs (i.e. out of pocket expenses) and work-related absence associated with accompanying a patient with FD for their administration of a single dose of ERT (with agalsidase alfa or agalsidase beta).
- To describe patient-reported HRQoL (measured by the 12 Item Short Form Survey [SF-12]), wellbeing (measured by the World Health Organization-5 Wellbeing Index [WHO-5]), levels of fatigue (measured by a bespoke Fatigue Likert scale) and work productivity (measured by the Work Productivity and Activity Index [WPAI] questionnaire) in patients with FD treated with ERT.
- To describe work productivity (measured by the WPAI for caregivers [WPAI:CG]) and the strain of care provision (measured by Caregiver Strain Index [CSI]).

2. STATISTICAL ANALYSIS

OpenHealth will carry out the statistical analysis for this project on behalf of Amicus. Analysis will be performed in R statistical software version 3.4.1, Stata™ (StataCorp LLC) version 14 and/or Microsoft Excel™.

2.1 Populations for analysis

Patients with FD who are receiving ERT and their caregivers from approximately 12 specialist centres in four countries (Taiwan, Turkey, Brazil and Japan) will form the sample for this study. In total, this study will have 240 ERT episodes, which includes 60 ERT episodes (30 for agalsidase alfa and 30 for agalsidase beta) in each participating country. Ideally, a maximum of two ERT administration episodes will be observed per patient; as such, at least 30 patients are expected to be enrolled in each country. For countries with limited FD patient numbers, a review of episodes of care observed will be completed on an ongoing basis. It may be determined that it is possible to observe three episodes per patient in these circumstances, however only two episodes will be observed per patient wherever possible.

2.2 Key definitions

Episode of care: An episode of care is an element or part of the care or treatment pathway which is being studied or measured. For the purpose of this study, an episode of care will constitute all healthcare professional (HCP) activities involved in the preparation and administration of a single dose of enzyme replacement therapy (ERT) with agalsidase alfa and agalsidase beta, including ERT (and pre-medication) preparation, pre- and post-administration assessment, pharmacy and clinic activities, and any follow up activities.

Caregiver: in the context of this study a caregiver is defined as an individual aged 18 years or over who has a personal relationship with and provides informal (unpaid) care, support or assistance to someone diagnosed with Fabry Disease, and accompanies them to the hospital or treatment centre for ERT administration on one or more occasion during the study data collection period. For example, this may be a parent, spouse/ partner, son/ daughter, other relative, neighbour or friend.

2.3 Missing Data

Where dates are ambiguous because of missing day and/or months, standard imputation will be applied: where day is missing the 15th of the month will be assumed; where both day and month are missing the 1st July will be assumed.

For other missing data, the affected analyses will be conducted using only the results of those patients/episodes with data available and the number included in each analysis will be stated.

The number of patients or caregivers with data missing will be reported for each study variable.

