	
with FD; stratified by country and by ERT product (agalsidase alfa or agalsidase beta).
 
Main secondary endpoints:
 
 ● Summary measures of the time spent by HCPs on each separate task associated with the preparation and administration of a single dose of ERT (with agalsidase alfa or agalsidase beta). ● Summary measures of the total patient time and costs associated with attendance for the administration of a single dose of ERT (with agalsidase alfa or agalsidase beta). ● Proportion of patients with work absence due to attendance for this ERT episode and number of hours absent. ● Summary measures of the total caregiver time and costs associated with accompanying a patient with FD for the administration of a single dose of ERT (with agalsidase alfa or agalsidase beta). ● Proportion of caregivers with work absence due to accompanying the patient for this ERT episode and number of hours absent. ● Summary measures of patients': 
 ○ HRQoL (SF-12 scores / responses). ○ General wellbeing (WHO-5 scores / responses). ○ Level of fatigue (Fatigue Likert scale) ○ Levels of work impairment (WPAI scores / responses). ● Summary measures of caregivers': 
 ○ Levels of work impairment (WPAI-CG scores / responses). ○ Level of strain in providing care for a patient with FD (CSI scores / responses).
--	---

5. Study amendments and updates

All amendments to the protocol will be documented in Table 1.

Protocol deviations will be documented in a Protocol Deviation Log (maintained in a separate document).

Table 1. Study amendments

Amendment number	Date of amendment	Section amended	Amendment description	Reason for amendment
1	Click here to enter a date.		None at present	
2	Click here to enter a date.			
3	Click here to enter a date.			
4	Click here to enter a date.			

6. Milestones

Table 2. Study milestones

Milestone	Planned date(s)/frequency
Planned regulatory approval activities	Start: Jun 2019 End: Aug 2020
Planned start of study (date of first consent)	Jun 2020
Planned collection of first data point	Jun 2020
Planned collection of last data point	Nov 2020
Study progress report 1	No progress report is planned
Interim study report 1	No interim analysis is planned
Registration in EU Post-authorisation study Register or equivalent public database	Clinical trials.gov; Feb 2020
Final report of study results (end of study)	Apr 2021

7. Rationale and background

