9.4.1 Selection criteria for patients

Patient inclusion criteria

- Patients aged 18 years old or over at time of consent.

- Patients with a documented diagnosis of FD.
- Patients who have received ≥4 doses of ERT (with agalsidase alfa or agalsidase beta) for the treatment of FD.
- Patients who present to the participating hospital(s) or treatment centre(s) for administration of a dose of ERT (as part of their routine treatment) during the data collection period.

Patients who meet any of the following criteria will be excluded:

- Patients aged <18 years at time of consent
- Patients who are unable or unwilling to give consent for study participation.
- Patients for whom ERT preparation and administration takes place exclusively in the home setting.
- *For the time and motion evaluation:* Patients whose ERT is administered by a HCP who does not consent to be observed.

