
Summary measures of (at date of consent, unless specified):
 
 • Sex. • Age at onset of first symptoms, at FD diagnosis and at date of consent. • Duration of ERT treatment. • ERT treatment. • FD phenotype (organs involved). • FD mutation ((if known)). • Severity of FD (to be determined using the specified baseline information]). • Any other relatives (with whom the patient lives) with FD. • Number and type (agalsidase alfa / agalsidase beta) of ERT infusions received in the year prior to date of enrolment. 	
 • Sex (male / female). • Date of consent. • Age at consent. • Age at onset of first symptoms. • Date of FD diagnosis. • ERT start date. • ERT treatment under observation (agalsidase alfa / agalsidase beta). • Number of ERT infusions received in the year prior to date of enrolment, by type of treatment (agalsidase alfa, agalsidase beta). • FD phenotype (organ involvement/complications), to include any current or prior history of: hypohidrosis, neuropathic pain (and/or acroparesthesia and/or acute pain crises), cornea verticillata, angiokeratomas, hearing impairment (including deafness and/or tinnitus), cardiac events (including rhythm and/or conduction disturbances, hypertrophic cardiomyopathy or left ventricular mass index [LVMi] above normal range, myocardial infarction

	
[MI], unstable angina, congestive heart failure, major cardiac medical procedures), renal events (including reduced estimated glomerular filtration rate [eGFR], abnormal albumin creatinine ratio [ACR], proteinuria or albuminuria, dialysis, kidney transplant), central nervous system (CNS) involvement (including brain magnetic resonance imaging [MRI] changes [white matter lesions], transient ischaemic attack [TIA] or stroke), FD-related gastrointestinal [GI] symptoms, plasma lyso-Gb3 levels above normal, low white blood cells (WBC) alpha-galactosidase, other: specify)
 
• eGFR at enrolment (closest measurement prior and preferably within 12 months); date and measurement.• Urine protein levels at enrolment (closest measurement prior); date and measurement.• WBC alpha-galactosidase (closest prior to enrolment); date and measurement• LVMi at enrolment (closest measurement prior and preferably within 12 months); date and measurement.
--	---

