
Summary measures of (at date of consent, unless specified):
 
 ○ Sex (male / female). ○ Age at consent. ○ Age at onset of first symptoms. ○ Levels of strain of providing care for a patient with FD (CSI scores / responses). ○ Duration of ERT treatment. ○ ERT start date. ○ ERT treatment under observation (agalsidase alfa / agalsidase beta). ○ Number of ERT infusions received in the year prior to date of enrolment, by type 	
Frequency distribution with percentages will be given.
 
Mean age with standard deviation along with other summary measures for quantitative variables as in section 2.5 will be calculated.
 
The total scores will be summarized as per section 2.5 for quantitative variables. The individual item responses will be presented using frequency and percentages.
 
The difference between ERT start date and end date will be calculated. The summary statistics for duration of ERT treatment will be given as per in section 2.5 for quantitative variables.
 
The number and percentage for the number of treatments for each type of treatment will be calculated as per section 2.5.
 
The frequency and percentages will be provided for each type of prior history.

of treatment (agalsidase alfa, agalsidase beta).
 
 ○ FD phenotype (organ involvement/complications), to include any current or prior history. ○ eGFR at enrolment (closest measurement prior and preferably within 12 months); date and measurement. ○ Urine protein levels at enrolment (closest measurement prior); date and measurement. ○ WBC alpha-galactosidase (closest prior to enrolment); date and measurement ○ LVMi at enrolment (closest measurement prior and preferably within 12 months); date and measurement. ○ FD mutation (name of mutation, if known, including: e.g. A143T) ○ Severity of FD (mild / moderate / severe) ○ Do any other relatives with whom the patient lives have FD (Yes / No / Not known). 	
Summary statistics for quantitative variables as described in section 2.5 will be provided for these variables.
 
Frequency distribution along with its percentages will be calculated for these variables.

--	---

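### The rule for partial dates has no limits, so an imputed ERT start can fall after consent or before diagnosis and distort the reported ERT duration

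*SAP*

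**What the plan says.** SAP 2.3 (Missing Data) gives two defaults for partial dates: "where day is missing the 15th of the month will be assumed", and "where both day and month are missing the 1st July will be assumed". Protocol 9.9.3 gives the same rule. Neither section makes the default conditional on another date, or says what to do if the result is impossible.

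The dates concerned are in Protocol 9.6, Table 4. The dataset includes the ERT start date, the date of consent and "Date of FD diagnosis". The planned summaries include duration of ERT treatment and "Age at onset of first symptoms, at FD diagnosis and at date of consent", and the table takes characteristics at the date of consent unless it says otherwise.

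For ERT duration, SAP 2.6 says: "The difference between ERT start date and end date will be calculated". It does not define that end date, and Table 4 collects none.

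Two other parts of the plan limit which dates are possible. The milestones (Protocol section 6, Table 2) plan first consent for June 2020 and the last data point for November 2020. Protocol 9.4.1 admits "Patients who have received ≥4 doses of ERT (with agalsidase alfa or agalsidase beta) for the treatment of FD", and Protocol section 7 describes both products as given every two weeks.

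**The concern.** A fixed default is sensible when nothing else is known about a date. Here the study usually does know more: the patient was on ERT before taking part, and was presumably diagnosed no later than treatment began. A rule that ignores those facts can produce values that cannot be true.

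What is at stake is a baseline descriptor. SAP 2.5 reports the range, so one negative ERT duration could appear as the minimum. It also allows geometric means, which cannot be calculated with a zero or negative value. Without a stated rule, someone would have to decide how to repair such a value after seeing the data.

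**Working it through.** The plan gives no figure to reproduce, so the check is calendar arithmetic.

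**Inputs**
- Defaults: 15th of the month, or 1 July (SAP 2.3, Protocol 9.9.3).
- Consent dates: 1 June to 30 November 2020 (Protocol Table 2; the last data point is used as the outer limit).
- Four doses two weeks apart span 3 x 14 = 42 days (Protocol 9.4.1 and section 7). This assumes that the spacing was kept and that the four doses came before consent.
- Assumption: ERT duration = consent date - ERT start date.
- Assumption: the true diagnosis date is not later than the true ERT start.

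**ERT start against consent, 1 July rule.** A start recorded only as 2020 becomes 1 July 2020.
- Consent 1 June: 1 June - 1 July = -30 days. Consent 30 June: -1 day. Every June consent gives a negative duration.
- Consent 1 July: 0 days. Consent 11 August: 41 days. All values in this span are below 42.
- From 12 August the imputed duration is 42 days or more.

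If recruitment slipped into January to June of another year, year-only starts in that year would behave the same way. The worst case is about -140 days, for a consent on 12 February (42 days after 1 January).

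**ERT start against consent, 15th rule.** The default moves a date at most 14 days later (from the 1st to the 15th). The shortest imputed duration is therefore 42 - 14 = 28 days. It is below 42 but not negative, and it stays non-negative for any true start at least 14 days before consent. The error in duration runs from -14 to +16 days.

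**ERT start against diagnosis, only the ERT start partial**
- 1 July rule, diagnosis later in the same year: the largest gap is 31 December - 1 July = 183 days. Example: diagnosis 10 September 2015 and start recorded as 2015 gives 1 July 2015, 71 days before diagnosis.
- 15th rule, diagnosis later in the same month: the largest gap is 31 - 15 = 16 days. Example: diagnosis 20 May 2015 and start recorded as May 2015 gives 15 May, 5 days before diagnosis.

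In both cases the true start is on or after diagnosis, so the reported ERT duration is too long by at least the gap.

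**Only the diagnosis date partial.** The order can reverse here too, by up to 181 days (1 January to 1 July in a non-leap year) or 14 days (1st to 15th). ERT duration is not affected. Age at diagnosis could be, and that is a planned summary in Protocol Table 4 but is not listed in SAP 2.6.

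**The case against.** **The triggering patient is unlikely.** A negative duration needs someone who started ERT within about six months of a June 2020 consent and whose site knows only the year. Table 4 asks for the number of infusions in the year before enrolment, by product, and Protocol 9.5 identifies patients from local databases and pharmacy records. A site with those records would normally know the month. Regulatory approvals run to August 2020, so June consents may come from only some sites. This stands, and it is why the point is minor. It weighs less on the diagnosis problem, because year-only dates are more likely for starts long ago.

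**Other checks may catch it.** Protocol 9.10 provides manual and programmed validation, with queries on out-of-range and inconsistent values, under a data management plan that is not among the documents. That may help. But a start recorded as 2020 is not itself out of range; the impossible value appears only once the default is applied. SAP 3.2 limits independent review to the primary endpoint and says no further analysis checks will be made.

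**Every single-date default carries error.** This is true: a year-only date can be wrong by about six months under any such rule. Limits remove only the impossible values.

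**Stronger readings that the documents do not support.** A reader might infer that both defaults can give negative durations. Under the planned calendar only the 1 July default does. A reader might also infer that the interval or order from diagnosis to treatment is a reported result. No such summary is planned in Protocol 9.6 or SAP 2.6, so a reversed order shows only as an inconsistency and through its effect on ERT duration or age at diagnosis.

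**Conclusion.** The point holds as a minor one. Followed literally, the rule gives an impossible ERT duration (-30 to -1 days) for a June 2020 consent with a start known only as 2020. It gives an implausible one (0 to 41 days) for consents from 1 July to 11 August 2020. It also overstates duration when a partial start is placed before a known diagnosis, by at least a gap that can reach 183 days under the 1 July rule and 16 days under the 15th rule.

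The figures against consent rest on reading the undefined end date as the date of consent. The figures against diagnosis rest on diagnosis not following treatment. The word implausible, rather than ineligible, is deliberate: 42 days is inferred from two-weekly spacing, and the inclusion criterion does not tie the four doses to the consent date. The negative durations do not depend on that inference.

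The documents do not say how many dates will be partial. Few patients, possibly none, will be affected. The primary endpoint uses observed clock times and does not change.

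**What to change.** Add to SAP 2.3 and Protocol 9.9.3:

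> *An imputed ERT start date may not be earlier than a known diagnosis date or later than the date of consent. An imputed diagnosis date may not be later than a known ERT start date. If the default falls outside the allowed interval within the recorded year or month, the midpoint of that interval is used. If both dates are partial, ERT start is imputed first, not earlier than the first day that the diagnosis record allows, and is then treated as known. The number of imputed dates is reported.*

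The first-day clause prevents an empty interval, for example when the start is known only as 2015 and the diagnosis as September 2015.

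In SAP 2.6, define the end date for ERT duration as the date of consent.

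Illustration: for consent on 10 June 2020 and a start recorded as 2020, the present rule gives -21 days. The allowed interval is 1 January to 10 June, 161 days long, so its midpoint gives a duration of 161 / 2 = about 80 days.

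The limit deliberately uses consent rather than consent minus 42 days, so the 0 to 41 day values for consents from 1 July to 11 August would remain. Reporting the number of imputed dates shows whether that matters. The cost is a short paragraph and a few lines of extra programming.
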